### 3.1.1 Ongoing Safety Assessment and Dose-Limiting Toxicity

AEs will be reported from the time of informed consent signature up to 30 days after the last dose of study drug or until the initiation of new anti-cancer treatment, whichever is sooner. SAEs will be reported until 90 days after the last dose of study drug, or until the initiation of new anti-cancer treatment, whichever is sooner. The period considered for DLT assessment for Part 1 is defined as the time from the first dose administration of AGI-134 and up to the end of the first cycle of therapy (i.e. Cycle 1/Day 1 to Cycle 1/Day 21).

agalin A subsidiary of BIG	PRIVILEGED & CONFIDENTIAL
Investigational Product: AGI-134	Protocol No. AGI-134.FIM.101
Phase: I/IIa	Version 6.1 31 May 2021

The period considered for DLT assessment for Part 2 is defined as the time from the first dose administration of AGI-134 and up to the end of the first cycle of therapy (i.e. Cycle 1/Day 1 to Cycle 1/Day 21) for the first 3 subjects with deep lesions.

After the DLT assessment period, data will be assessed on an ongoing basis during the study. All AEs should be captured within the eCRF, however AEs reported beyond the DLT period will not be considered for the DLT assessment.

During Part 2 of the study, any specific AE that fits the DLT definition and occurs at a frequency of > 30% will stop accrual. In this scenario, the Safety Committee may recommend a lower dose level or dosing schedule change for the continuation of the expanded cohort. The study will be discontinued or terminated in case of an unacceptable risk or a negative change in the risk/benefit assessment. This might include the occurrence of adverse events for which character, severity or frequency is unexpected and overcome the potential benefit of the study drug. In addition, any data deriving from other clinical trials or toxicological studies which negatively influence the risk/benefit assessment might cause discontinuation or termination of the study.

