#### ECG assessment:

- A 12-lead ECG Holter recording device will be connected to the subject 1-2 hours prior to AGI-134 administration and record ECG consecutively for at least 24 hours post AGI-134 administration.
- ECG printouts for safety assessment will be extracted prior to AGI-134 administration (up to 1 hour before dose) and 2 hours post dose (± 30 minutes).
- Symptom-directed physical examination pre-dose only
- Examination of injection- site will be performed 1 hour (±30 min) pre-AGI-134 administration, 1 hour (±30 min)
- Vital signs will be performed up to 1 hour pre-AGI-134 administration and 0.5, 1, 24, 36, 48 and 72 hrs post AGI-134 administration.
- ECOG performance status
- Photography of superficial injected and non-injected lesions will be performed 1 hour pre-AGI-134 administration (±30 min), 1 hour (±30 min)
- Review general instructions before study drug administration (see section 5.7)
- AGI-134 administration on Day 1
- Blood will be drawn for:
  - o CH50 pre-dose
  - o C5a pre-dose, 2 and 6 hours post AGI-134 administration
  - o Flow cytometry pre-dose and 24 hours post AGI-134 administration
  - O Cytokines pre-dose, 2, 6, 12 and 24 hours post AGI-134 administration
  - Anti-Gal antibodies IgG/IgM and sub classing pre-dose
  - PBMC isolation + cryopreservation pre-dose
  - Human leukocyte antigen (HLA) and MHCII haplotyping pre-dose
  - DNA isolation (MSI/dMMR/TMB, WES) pre-dose
  - TCR Sequencing pre-dose
  - RNA isolation (Gene expression/sequencing) pre-dose
  - PK of AGI-134 and metabolites: up to 1 hour prior to AGI-134 administration and at 0.5, 1, 2, 4, 6, 8, 12, 24, 36, 48 and 72 hrs post AGI-134 administration.
     For detailed time window for sample collection refer to the Laboratory Manual.

## 5.3.2 Cycle 1 - Day 3

- Blood will be drawn for:
  - o CBC with differential 48-72 hrs post AGI-134 administration
  - o Biochemistry Panel 48-72 hrs post AGI-134 administration
  - Cytokines: 48hrs post AGI-134 administration
  - RNA isolation (Gene expression/sequencing) 48±24hrs post AGI-134 administration
  - o PBMC isolation + cryopreservation: 48 ±24 hrs post AGI-134 administration

agalin A subsidiary of Bio	nnune DLINERX	PRIVILEGED & CONFIDENTIAL
Investigational Product: AGI-134		Protocol No. AGI-134.FIM.101
Phase: I/IIa		Version 6.1 31 May 2021

- Photography of superficial injected lesions prior to tumour tissue biopsy, if applicable
- Examination of injection prior to tumour tissue biopsy, if applicable

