- Tumour tissue biopsy will be performed 48 ±24 hrs post AGI-134 administration, from injected lesions only. This biopsy is mandatory for superficial injected lesion and is also requested for deep lesions, unless it is not considered in the best interest for the patient by the PI.

## 5.3.3 Cycle 1 - Day 8 and Day 15

The following procedures will be performed:

- Review of change in concomitant medication
- AE Recordings
- Symptom-directed physical examination
- Examination of injection site
- Photography of superficial injected and non-injected lesions if applicable
- Vital signs (blood pressures, pulse rate, O2 saturation, oral temperature in °C, respiratory rate)
- Blood will be drawn for:
  - CBC with differential
  - Biochemistry panel
  - o Anti-Gal antibodies IgG/IgM (Cycle 1 Day 8 only)

## 5.3.4 Cycles 2, 3 and 4

AGI-134 will be administered on Day 1 of each cycle. The following procedures will be performed during these visits; each assessment should be performed before administration of the investigational product unless otherwise specified. Detailed activities are presented in the SoA (APPENDIX A).

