# 8.3 Ongoing Safety Assessment and Dose-Limiting Toxicity

AEs will be reported from the time of informed consent signature and up to 30 days after the last dose of study drug or until the initiation of new anti-cancer treatment, whichever is sooner. SAEs will be recorded up to 90 days following the last dose of study drug or until the subject initiates new anti-cancer therapy, whichever is earlier.

The period considered for dose-limiting toxicity (DLT) and safety assessment for the accelerated escalation is defined as the time from the first dose administration of AGI-134 and up to the end of the first cycle of therapy (i.e. Cycle 1 - Day 1 through Cycle 1 - Day 21). Data will be reviewed by the Safety Committee. The Safety Committee will be composed of the Study PI together with the Sponsor's MM and Pharmacovigilance Manager (PhV) or designee which will be responsible for the review of all the safety data at pre-defined time points during Part 1 and 2. Safety will be monitored throughout the study.

Beyond the DLT assessment period, data will be assessed continually on an ongoing basis. AEs reported beyond the DLT assessment period will be captured within the eCRF, however will not be considered for DLT assessment period. During Part 2 of the study, any specific AE that fits the DLT definition, occurring at a frequency of >30% will stop accrual. In this situation, the Safety Committee may recommend a lower dose level or dosing schedule change for the continuation of AGI-134 at the RP2D.

Sites will be required to contact the Sponsor within 24 hrs if subjects present with an AGI-134 related AE that is moderate or higher grade and clinically significant or experience DLTs during the DLT assessment period (see Section 3.1.1).

A subject that dropped out of the study will be included in all relevant data analyses and presentation as described in the statistical section.

20		PRIVILEGED & CONFIDENTIAL
Investigational Product: AGI-134	A Phase I/IIa, multicentre, two-parts, open label study designed to evaluate the safety and tolerability of escalating	Protocol No. AGI-134.FIM.101
Phase: I/IIa		Version 6.1 31 May 2021

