# 8.3.3 Definition of Dose-Limiting Toxicity

A dose-limiting toxicity (DLT) is defined as a clinically significant AEs or abnormal laboratory value assessed as unrelated to disease progression, intercurrent illness or concomitant medications, occurring after at least one dose of investigational product during the DLT assessment period (see Section 3.1.1) and meeting any of the following criteria:

- CTCAE Grade 3 AST (SGOT) or ALT (SGPT) or bilirubin for ≥7 days
- CTCAE Grade 4 AST (SGOT) or ALT (SGPT) of any duration
- CTCAE Grade 3 or higher febrile neutropenia, neutropenia or thrombocytopenia
- CTCAE Grade 4 (life-threatening) vomiting or diarrhoea, regardless of response to management.
- CTCAE Grade 4 electrolyte abnormalities, regardless of response to management.
- All other, AEs CTCAE Grade 4.
- All other AEs Grade 3 with the following exceptions: Transient (less than 24 hours within injection time) nausea and vomiting, investigational product-related fever, electrolyte abnormalities (including K, Na, Cl, HCO3, Mg, Ca) anorexia and alopecia.

To be considered a DLT, the toxicity should be assessed as at least possibly related to the investigational product.

An AE must be clinically significant to be defined as a DLT (e.g. nausea and vomiting, investigational product-related fever, electrolyte abnormalities (including K, Na, Cl, HCO3, Mg, Ca) that are ≤ Grade 3 will not constitute a DLT).

V2		PRIVILEGED & CONFIDENTIAL
Investigational Product: AGI-134	A Phase I/IIa, multicentre, two-parts, open label study designed to evaluate the safety and tolerability of escalating	Protocol No. AGI-134.FIM.101
Phase: I/IIa		Version 6.1 31 May 2021

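### DLTs are defined by date of occurrence but excluded by date of report, and no safety labs are scheduled for Days 16-21, so the plan does not settle whether a dose-1 toxicity first seen on Day 22 counts.

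*Combined protocol and SAP*

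**What the plan says.** **Window.** For Part 1, Section 3.1.1 sets the DLT period as first dose "up to the end of the first cycle of therapy (i.e. Cycle 1/Day 1 to Cycle 1/Day 21"). The same days apply to the first 3 deep-lesion subjects in Part 2.

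**Exclusion, keyed to reporting.** Section 3.1.1 and the Synopsis: "AEs reported beyond the DLT period will not be considered for the DLT assessment". Section 8.3: "AEs reported beyond the DLT assessment period will be captured within the eCRF, however will not be considered for DLT assessment period".

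**Definition, keyed to occurrence.** Section 8.3.3 covers an event "occurring after at least one dose of investigational product during the DLT assessment period (see Section 3.1.1").

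**Laboratory criteria.** Section 8.3.3 includes "CTCAE Grade 3 or higher febrile neutropenia, neutropenia or thrombocytopenia", with no duration condition, and "CTCAE Grade 3 AST (SGOT) or ALT (SGPT) or bilirubin for ≥7 days".

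**Lab schedule.** The first post-dose Cycle 1 panel is at Day 3 ("CBC with differential 48-72 hrs post AGI-134 administration", and likewise for biochemistry; the Part 1 table gives 72 hours). The remaining Cycle 1 panels are on Days 8 and 15 (Section 5.3.3; Tables 6 and 7), each with a +3-day window. The next panel is pre-dose on Cycle 2 Day 1, with a ±3-day window. Cycles last 3 weeks and may be extended for safety evaluation (Synopsis; Section 5.3).

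**The concern.** A cut-off based on when an event is reported works only if everything arising in the window is also looked for in the window. Here the last planned look is Day 15 and the next is nominally one day after the window closes. Neutropenia that develops on Day 19 and is found in the pre-dose sample on Day 22 is a consequence of dose 1, since dose 2 has not been given. Section 8.3.3 would count it; Sections 3.1.1 and 8.3 would not. The same applies to a symptom from Day 20 first mentioned at the Cycle 2 Day 1 visit. Two committees could read the same patient differently.

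Much rests on the count. MTD and RP2D are part of the primary endpoint. Part 1 starts with one subject per dose level, so a single uncounted DLT can decide an escalation. The Part 2 deep-lesion check begins with 3 subjects and uses the same window. An omitted event always pushes towards escalation or clearance.

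**Working it through.** The plan states no operating characteristics for the DLT rule. Its only related figure, the Part 1 maximum of 24 (Section 8.1), reproduces as 4 dose groups × 6 subjects. The rest is calendar arithmetic followed by an illustration.

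**1. Days without a scheduled lab**
- Cycle 2 Day 1 = 1 + 21 = Day 22.
- Nominal draws: Day 3 (48-72 h), Day 8, Day 15, Day 22. The window closes on Day 21.
- Days 16-21 have no scheduled lab: 6/21 = 28.6% of the window.
- With the visit windows, the Day 15 draw can fall on Days 15-18 and the Cycle 2 Day 1 draw on Days 19-25. The latter can land inside the DLT period (Days 19-21) but need not.

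**2. Grade 3 liver value first seen at the Day 15 visit**

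| Day 15 visit draw | Cycle 2 Day 1 draw | Days apart | Ends by Day 21? | At least 7 days and by Day 21? |
|---|---|---|---|---|
| 15 | 19 | 4 | yes | no |
| 15 | 22 | 7 | no | no |
| 15 | 25 | 10 | no | no |
| 18 | 19 | 1 | yes | no |
| 18 | 22 | 4 | no | no |
| 18 | 25 | 7 | no | no |

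The longest span that still ends in the window is Day 15 to Day 21, 6 days apart. Scheduled draws therefore cannot confirm such a value by Day 21. By contrast, a value first seen on Day 8 can be confirmed on Day 15 (15 − 8 = 7). Whatever the testing, 7 elapsed days by Day 21 require onset by Day 14 (21 − 7), or Day 15 if both end days count (21 − 6). An onset after Day 15 cannot complete 7 days inside the window on either convention.

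**3. Possible effect on escalation**

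Assumptions, none taken from the plan: onset is uniform over 21 days; every laboratory DLT arising on Days 16-21 is missed; laboratory events are a share s of all DLTs, from 25% to 100%.
- Counted rate: p′ = p × (1 − s × 6/21).
- 3+3 clearance (0 of 3, or 1 of 3 then 0 of 3): P = (1 − p)³ + 3p(1 − p)² × (1 − p)³.

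Worked at p = 0.30:
- All DLTs counted: 0.343 + 0.151 = 0.494.
- s = 25%: p′ = 0.30 × (1 − 0.0714) = 0.279, P = 0.539.
- s = 100%: p′ = 0.30 × 15/21 = 0.214, P = 0.678.

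| True DLT rate | Clearance, all counted | s = 25% | s = 100% | One subject passes (1 − p), all counted | s = 25% | s = 100% |
|---|---|---|---|---|---|---|
| 20% | 70.9% | 73.9% | 82.8% | 80.0% | 81.4% | 85.7% |
| 30% | 49.4% | 53.9% | 67.8% | 70.0% | 72.1% | 78.6% |
| 33% | 43.4% | 48.1% | 63.1% | 67.0% | 69.4% | 76.4% |

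The single-subject columns cover the accelerated stage and consider DLTs only.

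**The case against.** A reader might infer that last-week laboratory DLTs and late liver DLTs cannot be counted at all. The documents do not support that:
- Section 8.3.3 goes by occurrence, so onset by Day 21 with detection on Day 22 fits the definition as written.
- Abnormal labs are repeated as clinically indicated (Section 5.8.6), unscheduled visits may include labs (Section 5.6), subjects are told to contact the site about changes in well-being (Section 5.2), and sites must alert the sponsor within 24 hours to relevant events (Sections 3.1 and 8.3).
- Cycle 2 Day 1 may fall on Days 19-21.
- The Synopsis gives the Day 1-21 limits only as an example of the first cycle, and a cycle may be extended.
- Section 8.3.3 does not say that the 7 liver days must finish by Day 21.

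Nor are DLTs the only input to escalation. A related, clinically significant moderate or worse Cycle 1 event also triggers expansion (Section 8.3.1), and the Safety Committee reviews all safety data.

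The 68% figure should not be read as an expected effect. It treats every DLT as a laboratory event, and the monkey study showed no drug-related haematology changes and no definitive chemistry changes (Section 1.1.1).

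All of this limits the size of the problem but does not remove it. Repeat testing follows a known abnormality; it does not find a silent one after a normal Day 15 panel. Unscheduled visits are discretionary, an early Cycle 2 visit is a matter of chance, and the plan gives cycle extension no stated effect on the DLT period. The conflict between occurrence and report stands untouched.

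**Conclusion.** The point holds as an internal conflict with a directional consequence. Whether a dose-1 event with onset by Day 21 but first seen or mentioned on Day 22 counts depends on unscheduled testing, visit timing and which section is followed. For the 7-day liver criterion, a value first seen at the Day 15 visit cannot be confirmed by Day 21 from scheduled draws, and the plan is silent on whether confirmation must come by then.

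The direction is certain: omitted events favour escalation. The size is not. At a true 30% rate, clearance moves from 49% to about 54% with a quarter of DLTs being laboratory events, and to 68% at most. Both figures assume uniform onset and that no Day 16-21 laboratory DLT is caught by unscheduled testing or an early Cycle 2 visit. This should be corrected, because it bears on the MTD, the RP2D and the deep-lesion check.

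**What to change.** Reconcile the Synopsis and Sections 3.1.1 and 8.3 with Section 8.3.3, so that the exclusion and the definition use one basis. Date of occurrence is the basis Section 8.3.3 already states; the exclusion sentences would then refer to events occurring, not reported, after the period. Also state:
- whether an event with onset in the period counts when its duration criterion is settled after Day 21;
- whether extending Cycle 1 changes the DLT period;
- whether the Cycle 2 Day 1 pre-dose labs, already scheduled, form part of the Safety Committee's Cycle 1 review.

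The length of the window is the sponsor's choice and is not proposed here. The cost is wording only, with no new sample or visit. The Committee's decision may have to wait briefly if Cycle 2 Day 1 results or an unresolved liver value are to be included.

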# Ongoing Safety Assessment and Dose-Limiting Toxicity

AEs will be reported from the time of informed consent signature Up to 30 days after the last dose of study drug or until the initiation of new anticancer treatment, whichever is sooner. SAEs will be reported until 90 days after the last dose of study drug, or until the initiation of new anticancer treatment, whichever is sooner.

agalin A subsidiary of Bit	OLINERX	PRIVILEGED & CONFIDENTIAL
Investigational Product: AGI-134		Protocol No. AGI-134.FIM.101
Phase: I/IIa	doses of AGI-134 in unresectable/metastatic solid tumours.	Version 6.1 31 May 2021

Study Assessments	The period considered for DLT assessment is defined for Part 1 and Part 2, as the time from the first dose administration of AGI-134 and up to the end of the first cycle of therapy (e.g., Cycle 1/Day 1 through to Cycle 1/Day 21).  After the DLT assessment period, data will be assessed an ongoing manner during the study. All AEs should be captured within the eCRF; AEs reported beyond the DLT period will not be considered for the DLT assessment.
	General instructions before study drug administration
	The following instructions should be followed before AGI-134 administration:
	
 
AGI-134 should only be administered when personnel and therapies are immediately available for the treatment of hypersensitivity reactions, should they occur. This should include having an open IV cannula and fluid therapy readily available.
 

	
 
Hypovolaemia, if present, should be corrected prior to administration of AGI 134 according to the study site standard of care.
 

	
 
For patients who receive routine anti-hypertensive medication, these medications should be withheld in the 24 hours prior to injection of AGI-134.
 

	Recommendations for patients who experience systemic reactions related to study drug are detailed in section 5.7.
Study	The duration of core study participation is 54 weeks.
Duration	A Termination visit will be performed for all subjects on Week 54. Long-term follow-up will continue for all subjects for up to 5 years.
	The study consists of the following study periods:
	Screening Period: up to 28 days
	Core Study: up to 54 weeks
	Long-Term Follow-Up: Following Termination/Early Termination visit, a follow-up telephone call will be performed to all subjects every 9 weeks up to 5 years in order to assess duration of response and survival.
Planned	Part 1: Up to 24 subjects.

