### 8.3.1 Part 1 – Accelerated Dose Escalation of AGI-134

At any given dose, if one subject presents with a dose-limiting toxicity (DLT) or an event of moderate or higher severity assessed as related to AGI-134 and as clinically significant during the first cycle of treatment, the group of subjects will be expanded and the study will continue in a conventional "3+3" design. The expansion after an event of moderate severity will be to a total of 3 subjects and the expansion after a DLT will be to a total of 6 subjects, recruited in a stepwise manner of 3+3. Moderate injection site reactions are expected events with any injectable drug, as are moderate drug administration-related fever, nausea and vomiting. These will therefore will not be considered as a trigger for conversion to a "3+3" design. If the group of subjects was expanded due to a clinically significant related event that is not a DLT, and this expanded group, i.e. 3 subjects, showed no DLT events, then the study will continue to the next dose level enrolling 3 subjects.

If 1 out of 3 subjects presented with a DLT in the expanded cohort, a group of additional 3 subjects will be treated at the same dose level. If no more DLTs are reported at that dose, i.e. only 1 out of a total of 6 subjects has developed a DLT, the dose escalation will continue to the next level. At any given dose, if 2 or more out of 6 subjects experience a DLT, that dose level will be considered as the DLT dose. In such a case, 3 more subjects will be administered at the previous dose level, if there are less than 6 subjects already treated at that dose. MTD is defined as the highest dose level in which 6 subjects have been administered with and less than 2 instances of DLT.

When the first subject in each dose completes the first cycle of treatment, (each Cycle is 3 weeks long), the safety and tolerability will be assessed by a Safety Committee to decide whether to escalate the dose or to expand the group of subjects. When the MTD is reached or the 200 mg dose is found to be safe, whichever comes first, it will be defined as the RP2D and the study will continue to Part 2.

After completion of the first treatment cycle, subjects in Part 1 of the study will continue receiving intratumoural injection at the dose determined at Screening for 3 additional cycles. No intra-subject escalation will be allowed. The treatment regimen is one dose per cycle of AGI-134 every three weeks for up to 4 cycles.

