### 8.3.2 Part 2 - AGI-134 at the RP2D

Safety interim analyses are planned after 3 subjects with deep injectable lesions have completed the first cycle with AGI-134 (i.e. Cycle 1 - Day 1 through to Cycle - Day 21). Sites will be required to contact the Sponsor within 24 hrs if a subject present with a DLT during the DLT assessment period (see Section 3.1.1).

During Part 2, 3 subjects will be evaluated after one cycle of injection into deep lesions. If one or more of the subjects experiences DLTs, a new assessment will be done after the additional 3 subjects with deep lesions injected are enrolled and treated (total 6 subjects). If no new DLTs are reported, the recruitment will continue as planned. If 2 or more subjects presented a DLT, the SC will assess the risk vs. benefit of the treatment and recommend whether or not the dose of AGI-134 should be reduced and/or the treatment schedule be changed (see Section 8.3).

Following the assessment of the first 3 patients with deep lesion injected or 6 patients if expansion is needed, the safety data will be evaluated by the Safety Committee. Evaluation by

agalin A subsidiary of Bio	nnune DLINERX	PRIVILEGED & CONFIDENTIAL
Investigational Product: AGI-134		Protocol No. AGI-134.FIM.101
Phase: I/IIa		Version 6.1 31 May 2021

the Safety Committee will be conducted every 6 months to review ongoing safety data, until the last patient last visit (LPLV).

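### Section 3.1.1 limits the Part 2 DLT period to the first three deep-lesion subjects, which contradicts the synopsis and the six-subject look and leaves unclear whose DLTs the >30% accrual stop counts

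*Combined protocol and SAP*

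**What the plan says.** The accrual stop appears twice in the body of the protocol. Section 3.1.1 says that in Part 2 "any specific AE that fits the DLT definition and occurs at a frequency of > 30% will stop accrual", and Section 8.3 repeats it: "any specific AE that fits the DLT definition, occurring at a frequency of >30% will stop accrual". Neither place gives a denominator, a minimum number of subjects or a schedule of checks.

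Section 8.3.3 defines a DLT as an event "occurring after at least one dose of investigational product during the DLT assessment period", refers to Section 3.1.1 for that period, and then lists the grade criteria.

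Section 3.1.1 sets the Part 2 period as Day 1 to Day 21 of Cycle 1 "for the first 3 subjects with deep lesions". It adds that AEs after the period are not used for DLT assessment. The synopsis differs: "The period considered for DLT assessment is defined for Part 1 and Part 2", with the same Cycle 1 window and no limit to particular subjects. Section 8.3 does not settle the matter, because it speaks only of Part 1: "The period considered for dose-limiting toxicity (DLT) and safety assessment for the accelerated escalation is defined as".

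Two other Part 2 provisions depend on the same definition. In Section 8.3.2, sites are "required to contact the Sponsor within 24 hrs if a subject present with a DLT during the DLT assessment period". The deep-lesion look (synopsis and Sections 3.1, 8.3.2 and 9.7) evaluates three deep-lesion subjects after one cycle and adds three more if any has a DLT. If two or more subjects have had a DLT, the Safety Committee reviews risk and benefit.

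**The concern.** Safety and tolerability is the primary objective of this first-in-human study. Part 1 may expose only one subject per dose level, so much of the experience at the RP2D will come from Part 2, which also brings the first injections into deep lesions. The >30% rule is the only numerical accrual stop meant for all of Part 2.

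A stopping rule has to say whose events count and over what denominator. Here the definition chain ends in a period that exists, on the words of the body text, for three subjects only. A site that sees a Grade 4 event in a superficial-lesion subject during Cycle 1 cannot tell from Sections 3.1.1 and 8.3.3 whether it is a DLT, whether the 24-hour DLT report applies, or whether it enters the >30% count.

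**Working it through.** **Inputs.** Part 2 sample size: approximately 35 (Section 8.1). Threshold: more than 30% (Sections 3.1.1 and 8.3). Part 2 DLT period: three deep-lesion subjects (Section 3.1.1). Deep-lesion look: three, then up to six subjects (Section 3.1). The plan states no operating characteristics for the stop, so there is no figure to reproduce.

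**Step 1: the chain.** The stop counts AEs that fit the DLT definition. The definition (8.3.3) includes timing within the DLT period. That period (3.1.1) is given in Part 2 for the first three deep-lesion subjects.

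**Step 2: who is left out on the literal words.** 35 − 3 = 32 subjects, and 32/35 = 91%. They include all superficial-lesion subjects and subjects 4 to 6 of the deep-lesion look.

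**Step 3: what the literal stop would do.** The protocol gives no denominator, so both candidates are shown.
- Denominator of the three assessable subjects: 1/3 = 33.3% > 30%. One DLT stops accrual, although the deep-lesion look responds to one DLT by adding three subjects.
- Denominator of all treated Part 2 subjects, with at most three countable: 3/9 = 33.3% fires, but 3/10 = 30.0% does not exceed 30%. The stop could not fire from the tenth subject on (3/35 = 8.6% at the end).

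The two denominators give opposite behaviour. The denominator therefore needs stating as well as the period.

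**Step 4: the stop with the period covering everyone.** At n = 35, 0.30 × 35 = 10.5, so 11 subjects with the same AE are needed (11/35 = 31.4%; 10/35 = 28.6% does not fire). At n = 10, four are needed.

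**Step 5: the separate matter of pooling.** The stop counts each AE term on its own. Part 1 counts subjects with any DLT ("if 2 or more out of 6 subjects experience a DLT, that dose level will be considered as the DLT dose"), and so does the deep-lesion look. To see how much this matters, assume N = 35, one DLT per affected subject, and a check after each subject from the 1st, 6th or 10th on, firing when count > 0.30 × n. The DLT rates, splits and check times are assumptions; the documents give none. Probability of firing, by simulation (100,000 draws per setting):

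| Any-DLT rate and split over three terms | Per-AE, from 1st / 6th / 10th | Pooled, from 1st / 6th / 10th |
|---|---|---|
| 40%, equal | 84% / 59% / 29% | 98% / 97% / 96% |
| 40%, 60/20/20 | 88% / 71% / 54% | 98% / 97% / 96% |
| 40%, 80/10/10 | 94% / 88% / 82% | 98% / 97% / 96% |
| 30%, equal | 70% / 37% / 12% | 88% / 82% / 76% |

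The deep-lesion look adds protection. With p the DLT rate and q = 1 − p, it reaches two or more DLTs with probability 1 − q³ − 3pq²·q³. At p = 0.40 this is 1 − 0.216 − 0.093 = 0.69. Combined with the stop (six deep-lesion subjects at random positions, 40%, equal terms), the chance that something fires is 93% / 84% / 75% per-AE against 99% / 98% / 98% pooled.

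Pooling has a price. Checked from the tenth subject, a pooled >30% rule fires in 4% of trials at a true 10% DLT rate and in 33% at 20%. Including the look (equal terms), the chance of any committee trigger rises from 9% to 12% and from 31% to 48%.

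**The case against.** **The literal reading defeats itself.** If only three subjects could have a DLT, subjects 4 to 6 of the deep-lesion look could not have one, yet the protocol assesses DLTs in all six. The limiting phrase may simply describe the start of that look, and the stop may mean any event that meets the grade criteria in any Part 2 subject. This stands as an argument about intent. It does not remove the problem, because Section 8.3.3 puts timing into the definition, Section 3.1.1 supplies that timing, and Section 8.3 supplies none for Part 2.

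**Other safeguards exist.** These are the deep-lesion look, six-monthly committee review, 24-hour SAE reporting for every subject and the unacceptable-risk clause in Section 3.1.1. This also stands. None of them is a numerical accrual stop, however, and the look covers at most six subjects, none with superficial lesions.

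**A Cycle 1 window for everyone could narrow the stop** if the sponsor meant Cycles 2 to 4 to count. Sections 3.1.1 and 8.3 already exclude later AEs from DLT assessment, so the synopsis window is the consistent choice. If later cycles are meant, the protocol should say so.

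**Per-AE counting is a legitimate choice.** A reader might infer from the Part 1 rule that the lack of pooling is an error. The documents do not support that. Per-AE counting sits beside a pooled deep-lesion look, and the gap shrinks when one term dominates or checks start early. Systemic injection reactions, for which Section 5.7 prepares, could be such a term. The level at which a specific AE is coded is also unstated, and grouping terms would narrow the gap further.

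**Conclusion.** The protocol contradicts itself on the Part 2 DLT period. On its words, Section 3.1.1 leaves about 32 of 35 subjects without a period in which a DLT can be counted. The synopsis and the six-subject look assume otherwise. This follows from the text and needs no assumption beyond the planned 35 subjects.

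A reader might go further and infer that the stop is designed to ignore 91% of subjects, or that it cannot fire from the tenth subject on. Neither is supported. The first reading would void the protocol's own six-subject look. The second depends on dividing by all treated subjects; with a denominator of three, a single DLT would stop accrual. What is established is an ambiguity in a safety rule that should be removed.

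Pooling is a trade-off. At an assumed 40% DLT rate, checked from the tenth subject, the per-AE stop fires in about 29% of trials with three equal terms and 82% with an 80/10/10 split, against 96% pooled. Those figures treat each 21-day outcome as known before the next check, so more subjects could already be on treatment when either rule fires.

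**What to change.** **Correction.** In Section 3.1.1 delete "for the first 3 subjects with deep lesions", so that the Part 2 DLT period is Day 1 to Day 21 of Cycle 1 for every treated Part 2 subject, as in the synopsis. In Sections 3.1.1 and 8.3 state that the >30% frequency is taken over all Part 2 subjects, superficial or deep, who have completed that period. A subject who leaves early because of a DLT should count as having completed it. Leave the three- and six-subject deep-lesion look as it is.

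The cost is one deletion and one clarifying sentence in two sections, made by protocol amendment. Part 2 already collects Cycle 1 AEs and Day 3, 8 and 15 blood tests, so no new data are needed.

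**Option, at the sponsor's discretion.** Keep the per-AE stop and add a pause for Safety Committee review if more than 30% of evaluated Part 2 subjects have had any DLT, checked from the tenth evaluated subject on. It would help most if DLTs spread over several terms. Its cost is more pauses, about 33% of trials at a true 20% DLT rate, each leading to review and not to termination.
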